3.4 Comparators

Three comparisons will be made:

1. When assessing treatment effectiveness, women with the infection who choose not to receive treatment will serve as the comparator (*untreated*). This comparator is a frequently preferred treatment option chosen by pregnant women due to their reluctance to use medications during pregnancy, based on their predominant concerns for the safety of their developing fetus as well as a lack of evidence that treating genital herpes infection is beneficial to their fetus. This comparator will also make the comparison groups more comparable by controlling for *confounding by indication*.
 2. When assessing the *timing of treatment effectiveness* (before vs. after the start of the 3rd trimester), those who receive treatment after the start of (during) the 3rd trimester will be used as the comparator. This comparator group will be comparable to those who receive treatment before the 3rd trimester, except for the timing of their treatment. Using this comparator will allow a *head-to-head comparison between the timing of the treatment (before vs. during the 3rd trimester)*
 3. When assessing the effect of choosing not to treat during pregnancy, women without an underlying genital herpes infection or receipt of any treatment will serve as the comparator (*normal controls*). This comparison will provide evidence of the increased risk of PTD and
-

LBW if genital herpes infection is *not* treated during pregnancy and will allow for a comprehensive assessment of comparative effectiveness of treating genital herpes.

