Treating pregnant women is unique in that it impacts *both* the mother and her developing fetus. CDC has highlighted a new initiative called "**Treating for Two**" and advocated research into medication use during pregnancy to take into account the effectiveness and risk-benefit profiles for both pregnant women and the developing fetus (<http://www.cdc.gov/pregnancy/meds/treatingfortwo/>)⁴². Currently, symptomatic genital herpes infection in pregnancy, usually considered more severe than asymptomatic genital herpes, is mostly treated with anti-herpes medications, such as acyclovir, that are effective in suppressing viral shedding and symptoms²³. Acyclovir is also recommended for treating genital herpes after 36 weeks of gestation to prevent vertical transmission of maternal herpes infection to the newborn^{23,24}. On the other hand, asymptomatic genital herpes before 36 weeks of gestation is often left untreated because of a lack of recognized benefits for fetal outcomes (e.g., reducing PTD and LBW). Thus, many women with mild or asymptomatic genital herpes are left untreated, and, consequently, at increased risk of PTD and LBW^{17,19-22}. Untreated genital herpes infection was associated with more than twice the risk of PTD and more than 40% of increased risk of LBW, compared to controls as described above. More importantly, if treated with acyclovir, women with genital herpes had a more than 50% reduced risk of PTD (OR=**0.49**, 95%CI=0.36-0.68), and 40% reduced risk of LBW (OR=**0.60**, 95%CI=0.37-0.98) than women who were not treated (Tables 2). Our preliminary results showed that the currently recommended treatment of herpes infection with acyclovir, if expanded to treat pregnant women with genital herpes before the 3rd trimester, could largely mitigate the risk of PTD and LBW associated with genital herpes infection. This treatment effectiveness was also consistent across subtypes of PTDs.

A lack of consistency in treating genital herpes infection in pregnant women is largely due to the knowledge gap regarding (1) increased risk of PTD and LBW associated with untreated

genital herpes infection in pregnant women, and (2) evidence of treatment effectiveness in reducing PTD and LBW, in addition to preventing mother-newborn vertical transmission of herpes infection^{17,19-21,35}.

A.4. Existing knowledge gaps

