A sample of 300 pregnant women from each of the four cohorts described above (Figure 1) will be randomly selected to form Stage II samples. The random selection will be spread evenly throughout the study period so that all of the estimated 90,000 participants in Stage I will have an equal chance of being selected. They will be selected after their inclusion in Stage I with known status of infection and treatment, mostly before the 3rd trimester to avoid interviewing after delivery to reduce participation and recall biases. Infection status will largely be known in the 1st or early 2nd trimester after the universal STD screening. Any change in exposure status (infection and treatment) after initial assignment will be rectified and finalized during analyses, as we have done in other similar studies with two-stage design (with different exposures in pregnancy).

Participants in Stage II samples will be interviewed to obtain more detailed information on characteristics of genital herpes infection, including history of the infection (e.g., age at initial infection, history of recurrence and treatment), whether it is a primary or latent infection, symptomatic or asymptomatic, etc. While our EMR has information on some of these characteristics of the infection, especially those ascertained through the prenatal screening tool, this Stage II interview will provide us additional characteristics of the infection to allow for assessment and thus to examine whether the treatment effectiveness varies depending on those infection characteristics (e.g., more effective for recent vs. past infection, and age at onset of initial infection, etc.).

The Stage II samples will also allow for direct ascertainment of compliance with prescribed medications. Studies based on pharmacy data alone usually have to make an assumption of 100% compliance with dispensed medications. In this study, we can directly examine the compliance and assess its potential impact on treatment effectiveness. This will be an important strength for this pharmacoepidemiologic study.

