Power calculations are based on the likelihood ratio test in the context of a Cox proportional hazards regression analysis for PTD, and a logistic regression analysis for LBW, as presented by Self⁵⁸ and as implemented in the software package EGRET⁵⁹. Given previous experience⁶⁰⁻⁶³, we expect negligible loss to follow-up (< 0.20%), a rate of PTD ranging from 8% - 12%⁶⁴, and LBW ranging from 8% to 10%⁶⁵. Each primary contrast of interest in analyses addressing **Aims 1, 2 and 5** can be characterized as a comparison of two groups of women with respect to risk of PTD and LBW. Minimum (maximum, for protective effects) detectable associations are of modest to moderate strength (Table 6). The proposed study will have more than sufficient power to detect the associations observed in our preliminary studies. Relevant to **Aim 3**, we present the maximum (protective effects assumed) detectable pattern of hazard ratios (HR) across cumulative treatment duration categories (no treatment, 1 – 10 days (45% among treated), > 10 days (55% among treated)). For the purpose of detectable effect calculations, we assume a graded, linear trend in (log) hazard/odds ratios across duration categories, a two-sided test for trend and a significance level of .05. We have sufficient power (.80) to detect a pattern of PTD HRs of 1.0 (ref), .82, and .67 associated with no treatment, 1-10 days and >10 days, respectively, assuming the worst case

scenario of expected 8% PTD rate. Similarly, we have sufficient power (.80) to detect a pattern of

Table 6. Minimum (maximum for protective scenarios) detectable hazard ratios (HR) for preterm delivery and detectable odds ratios (OR) for low birthweight in pair-wise comparisons of genital herpes exposure/treatment categories; two-sided test, significance level (α) = .05, power (1- β) =.80.

Contrast	Preterm Delivery (HR)		Low Birthweight (OR)	
	Rate = 8%	Rate = 11%	Rate = 8%	Rate = 10%
Treated infection vs. untreated infection (Aim 1; A+ B vs. C)	.71	.75	.70	.72
Treated < 3 rd trimester vs. 3 rd trimester (Aim 2, A vs. B)	.66	.71	.65	.68
Untreated infection vs. no infection (Aim 5, C vs. D)	1.51	1.40	1.54	1.47

odds ratios ORs of 1.0 (ref), .81, and .66 associated with no treatment, 1-10 days and >10 days, respectively, assuming the worst case scenario of expected 8% LBW rate.

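### Treatment and its timing follow symptoms, yet the plan calls late-treated women comparable except for timing and does not guarantee adjustment for infection type in Aims 1 and 2

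*Combined protocol and SAP*

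**What the plan says.** Section 3.4 makes two statements about comparators. For Aim 2 (A versus B) it is categorical: "This comparator group will be comparable to those who receive treatment before the 3rd trimester, except for the timing of their treatment". For Aim 1 (A+B versus C) it is relative: "This comparator will also make the comparison groups more comparable by controlling for" confounding by indication. Section 3.1 makes the same general claim and identifies the indication as genital herpes itself.

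Section A.3 describes who is treated. On one side, "symptomatic genital herpes infection in pregnancy, usually considered more severe than asymptomatic genital herpes, is mostly treated with anti-herpes medications". On the other, "asymptomatic genital herpes before 36 weeks of gestation is often left untreated because of a lack of recognized benefits for fetal outcomes". It adds that treatment after 36 weeks is recommended for a separate reason, to prevent transmission to the newborn.

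On measurement, section 3.3.3 collects symptomatic or asymptomatic status, primary or latent infection, and severity by interview in 300 women per cohort, and states an intention to control for differences in underlying infection. For Stage I it says only: "While our EMR has information on some of these characteristics of the infection".

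On analysis:
- Section 4.2 lists herpes history and characteristics among the Stage II explanatory variables. It names no covariate that must be in the Aim 1 or Aim 2 model. Candidates are factors plausibly linked to infection and PTD, kept if the treatment coefficient changes by 10% or more. Aim 2 adopts the same approach, and the low birthweight analyses run in parallel.
- Section 4.3 defines the propensity score as the probability of treatment versus no treatment. Its result becomes the main finding if it differs from the conventional one.

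**The concern.** Restricting the comparison to infected women removes confounding by infection. It does not remove confounding by the reason an infected woman is treated. On A.3's account that reason is largely symptoms and severity, and for late treatment it can be prevention of transmission. A may therefore hold more symptomatic women than B or C. The Aim 2 sentence in 3.4 conflicts with A.3, and the two need to be reconciled.

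The adjustment is also exposed at three points:
- The screening phrase asks whether a factor is linked to infection, whereas the exposure contrasted in Aims 1 and 2 is treatment or its timing among infected women.
- Whether the main indication enters the model depends on a data-driven rule.
- The propensity score does not model early versus late treatment, so Aim 2 has no propensity analysis built for its own contrast.

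If more severe infection raises PTD risk, the early-treated group starts at higher risk and a real benefit is understated. The sentence in 3.4 could also be carried into the conclusions as if it had been shown.

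**Working it through.** **1. The plan's own figures (4.5, Table 6).** Inputs: "two-sided test, significance level (α) = .05, power (1- β) =.80", and an effective 1,200 women per cohort. For PTD, detectable HR = exp(−(1.960 + 0.842)/√(d·q)), with d = total N × PTD rate and q = product of the two group fractions.

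| Contrast | PTD rate | d | q | HR computed | Table 6 |
|---|---|---|---|---|---|
| Aim 1, 2,400:1,200 | 8% | 288 | 2/9 | .705 | .71 |
| Aim 1 | 11% | 396 | 2/9 | .742 | .75 |
| Aim 2, 1,200:1,200 | 8% | 192 | 1/4 | .667 | .66 |
| Aim 2 | 11% | 264 | 1/4 | .708 | .71 |

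All agree within .01. A likelihood-ratio calculation for low birthweight gives .701/.725 (Aim 1) and .654/.681 (Aim 2), against .70/.72 and .65/.68. Table 6 is reproduced, so its .71 and .66 serve as reference effects below, with the preliminary odds ratio of .49 from A.3.

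**2. Bias if infection type were left out entirely.** The documents give neither the symptomatic share by cohort nor its PTD hazard ratio h. Assumptions: 60-80% symptomatic in A, 20-30% in B and C, h = 1.2-2.0. Factor = [1 + (h−1)p1] / [1 + (h−1)p0].

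*A versus B:*
- Low end (.6 v .3, h = 1.2): 1.12/1.06 = 1.06. A true .66 appears as .70.
- Middle (.8 v .2, h = 1.5): 1.4/1.1 = 1.27. It appears as .84.
- High end (.8 v .2, h = 2.0): 1.8/1.2 = 1.50. It appears as .99.

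*A+B versus C:* section 3.3.3 expects 2,100 women in each of A and B, so the treated share is the average, (.6+.3)/2 = .45 or (.8+.2)/2 = .50.
- Low end (.45 v .3, h = 1.2): 1.09/1.06 = 1.03. A true .71 appears as .73.
- High end (.50 v .2, h = 2.0): 1.5/1.2 = 1.25. It appears as .89.

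**3. What the 10% rule leaves if the change is measured without error.** Taking the adjusted coefficient as the base, the largest tolerated factor is exp(0.1 × |ln HR|):
- HR .71: exp(0.0342) = 1.035
- HR .66: exp(0.0416) = 1.042
- HR .49: exp(0.0713) = 1.074

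The middle case in step 2 shifts the coefficient by ln(1.273)/|ln .66| = 0.241/0.416 = 58%, so the rule would keep infection type.

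**4. The rule with sampling error.** A simulation (20,000 runs per case) estimated the infection-type effect from Stage II only (600 v 300 for Aim 1, 300 v 300 for Aim 2) at an 8% PTD rate, with assumed shares of .5 v .3 or .7 v .3. The crude coefficient was taken as known and used as the base. Chance that a true infection-type confounder is dropped (range over the two share pairs):

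| Contrast, true HR | h = 1.25 | h = 1.5 | h = 2.0 |
|---|---|---|---|
| Aim 1, .71 | 13-32% | 4-12% | under 1% |
| Aim 1, .49 | 31-62% | 15-38% | 2-8% |
| Aim 2, .66 | 16-36% | 7-19% | 1-3% |

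The bias left after a drop is 1.05-1.09 at h = 1.25, 1.09-1.17 at h = 1.5 and 1.15-1.31 at h = 2.0. This is approximate: EMR data on infection type in Stage I would make dropping less likely.

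**The case against.** The strongest reply is that the plan sees the problem. Section 3.3.3 collects the relevant characteristics in order to examine comparability of treated and untreated women and to control for differences. Section 4.2 puts those characteristics in the two-stage likelihood. The propensity score in 4.3 draws on all known factors affecting the outcome, with no 10% filter. Section 4.4 adds an instrumental-variable check. Aim 4 already estimates the treatment effect within levels of infection type. Table 5, the confounder list, is not in the text available here and may name infection type.

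Much of this stands, and it rules out several stronger readings that a reader might infer:
- *That 3.4 calls untreated women comparable to early-treated women.* It says only more comparable, which is fair relative to uninfected controls, and the Aim 1 contrast is A+B versus C.
- *That infection type is ignored outside Aim 4.* Sections 3.3.3, 4.1 and 4.2 say otherwise.
- *That Aims 1 and 2 are confounded unless infection type is forced in.* The 10% rule would usually retain a strong confounder.
- *That the factor of 1.50 applies to Aim 1.* Averaging A and B limits it to 1.25 under the same assumptions.

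What the reply does not supply is a commitment. Stating an intention to control is not specifying a model, and a Table 5 entry would still face the 10% rule. Section 4.3 does not say whether infection type, known in full only for Stage II women, enters the score. The comparability check in 3.3.3 concerns treated versus untreated women, and neither it nor the propensity score addresses A versus B. The instrumental-variable analysis informs interpretation only.

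**Conclusion.** The categorical sentence on late-treated women conflicts with A.3 and is unsupported. The claim that an infected comparator controls confounding by indication holds for infection status, not for severity. Control of infection type is planned but not guaranteed, and the gap is widest for Aim 2.

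The factors of 1.06-1.50 (A versus B) and 1.03-1.25 (A+B versus C) describe complete omission, which is not what the plan proposes. They rest on assumed shares and hazard ratios. Section A.2 reports raised risk for both symptomatic and asymptomatic infection and gives no contrast between them. Under the 10% rule without sampling error, the residual is about 1.04 at an HR of .66 and 1.07 at .49. The practical risk is a moderate confounder dropped by chance.

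A reader might infer that severity could create an apparent benefit. If severity raises PTD risk and treated women are more often symptomatic, the bias runs the other way, toward no benefit. This is a worthwhile correction, not a fatal flaw.

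**What to change.** 1. In 3.4, delete or qualify the sentence that A and B differ only in timing, and limit the untreated-comparator sentence to confounding by infection status. Align 3.1.
2. In 4.2, force pre-treatment infection type (symptomatic versus asymptomatic, primary versus recurrent) into the Aim 1 and Aim 2 models regardless of the 10% rule. Use the EMR measure where it exists and the interview measure through the two-stage likelihood. Status must predate treatment: A.3 says these drugs suppress symptoms, so later status could adjust away part of the effect.
3. In 4.3, include infection type in the propensity model and add an A-versus-B propensity model for Aim 2.
4. Report the balance of infection type across A, B and C.

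**Cost.** Plan wording and a few model terms. The interview items are already planned, but the EMR holds only some of these characteristics for Stage I women, so full adjustment leans on Stage II. Intervals widen by roughly 1/√(1−ρ²), where ρ is the correlation of infection type with the contrast. For A versus B, ρ² = .091 at 60% v 30% (about 5% wider) and .36 at 80% v 20% (25% wider). For A+B versus C, ρ² = .021 at 45% v 30% and .083 at 50% v 20% (about 1-4% wider). The formula that reproduces Table 6 has no term for this correlation. Under strong imbalance with a real effect of infection type, the 10% rule would usually have kept the variable anyway, so the added cost of forcing it in should be small.

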4 STATISTICAL METHODS

4.1 General Approach

The study design can be characterized as two-stage, with the first stage sample consisting of 90,000 pregnant women, each of whom will be classified into the four primary exposure categories defined by genital herpes and treatment status (Figure 1). In addition to exposure status, extensive potential confounders as described above (Table 5) will also be measured on the Stage I sample of 90,000 subjects. At the second stage, a random sample of 300 women will be selected within each of the four exposure categories (total N=1,200), for detailed history and characteristics of genital herpes infection, compliance to prescribed medications, and additional confounder/effect modifier assessment prior to delivery. Unlike typical applications of two-stage sampling in epidemiologic studies, where the Stage II sample is selected on the basis of both exposure (or exposure surrogate) and outcome (i.e. two stage case-control sampling), only exposure status will be known at the time of Stage II sampling to keep the nature of a cohort study design (*covariate assessment prior to pregnancy outcome assessment*). However, pregnancy outcomes of interest will eventually be measured on all 90,000 Stage I units, and *we will utilize all available information in both Stage I and Stage II samples in estimation of associations of interest*. Study Aims will be addressed using logistic regression (LBW) and Cox proportional hazards regression models (PTD)^{48,49}.

4.2 Estimation

Regression parameter estimates and associated standard errors will be obtained via semiparametric maximum likelihood (SMLE)⁵⁰ utilizing exposure, outcome, and confounder measurements on all 90,000 Stage I units in addition to the additional confounder/effect modifier measurements on the subset sample at Stage II. Thus, our study design can be characterized as a missing data problem, with Stage II covariates only assessed on a subset of the full cohort. Scott and Wild presented a unified method for fitting arbitrary regression models to a large class of missing data and/or response selective sampling problems. These applications are generally characterized as: 1) a set of easily-obtainable variables are measured on a sample of N individuals (Stage I); one or more of these variables are to be used as explanatory in the regression model (e.g. herpes and treatment status), or are informative surrogates for “expensive” variables to be measured on a subsample; 2) the response variable is obtained for all N individuals (e.g. LBW and PTD status) or a subset; and, 3) a set of “expensive” explanatory variables (e.g. details in genital herpes history and characteristic, compliance to treatment, and potential confounders/effect modifiers) are measured on a subsample (Stage II). Parameter estimation is by maximizing the profile likelihood (R software available from the authors), with the estimator shown to be consistent and have full semiparametric efficiency⁵⁰.

Aim 1. Does treating genital herpes infection in pregnant women reduce the risk of adverse pregnancy outcomes including PTD or LBW? (treated vs. untreated)

Point and interval estimates of the hazard ratio for PTD associated with treated genital herpes vs. not treated infection, will be calculated as described above, using Cox regression (Cohort A + B vs. C). In determining potential confounders in our regression models, we will first examine

risk factors that may be plausibly linked to infection and PTD. Inclusion or exclusion of potential confounding factors in our final regression models will be evaluated based on comparison of the regression coefficient associated with the contrast of interest (treated vs. untreated) both adjusted and unadjusted for the potential confounder under consideration (i.e. inclusion if regression coefficient changes by 10% or more). The change-in-estimate approach to confounder selection performs well with regard to power, bias, mean squared error and confidence interval coverage for the primary factor of interest⁴⁵. Continuous potential confounders will first be categorized either as quartiles, or into clinically relevant categories (e.g. BMI classification, amount of cigarette smoked or alcohol intake). The shape of the association/pattern of regression coefficients across increasing levels of the categorized covariate, of interest in their own right, will serve as a guide in the approach to modeling the variable as a continuous independent variable. A simple linear term may be appropriate, but higher order polynomial terms may be necessary to capture any non-linearity in association. Departures from model assumptions will be assessed via diagnostic plots of weighted residuals and tests for interaction between exposure and time (gestational age).

Analyses of LBW as the outcome will parallel those described above for PTD, but logistic regression techniques will be used rather than Cox regression, in Aims 1 – 5.

Aim 2. Does the timing of the treatment during pregnancy influence the treatment effectiveness on reducing adverse pregnancy outcomes (PTD and LBW)? (A head-to-head comparison of treatment timing: before the 3rd trimester vs. during the 3rd trimester).

Point and interval estimates of the relative hazards of PTD associated with first treatment during pregnancy before and first treatment during the 3rd trimester will be obtained (Cohort A vs. B) by extending the Aim 1 regression model to capture treatment timing. Parameter estimation, the approach to inclusion of potential confounders, modeling of continuous covariates, and model diagnostics are as described above for Aim 1 analyses. Treatment will be handled as a time-varying covariate for proper classification of exposure status in each risk set for the Cox regression (three levels: no treatment, first treatment < 3rd trimester, treatment in 3rd trimester). Significance of the difference between strength of association across the two treatment timing categories will be assessed via a Wald test.

Aim 3. Do other treatment metrics, including treatment duration, dosage, and compliance, impact treatment effectiveness in reducing PTD and LBW risk?

Metrics of treatment exposure of interest will be treated as time-dependent covariates in Cox regression analyses to account for changes in exposure status during follow-up, including cumulative duration (categorized as no use, 1-5 days, 6-10 days, 11-30 days, and > 30 days) based on clinical prescription patterns, and cumulative dose (categorized as no use, 1-4,800mg, 4,801-12,000mg, and >12,000 mg) also based on current clinical prescription patterns. In addition to examining these metrics in relation to pregnancy outcomes during the entire pregnancy, we will also assess trimester-specific measures of treatment duration and dose.

Aim 4. Does treatment effectiveness vary depending on the type (or severity) of underlying genital herpes infection? (e.g. treating symptomatic genital herpes infection vs. treating latent/asymptomatic genital herpes)

Analyses will examine potential heterogeneity in association between treatment and PTD across infection characteristics via the inclusion of appropriate cross-product terms and a likelihood ratio test, and point and interval estimates of association at each level of the effect modifier will be obtained via appropriate transformed linear combinations of regression parameter estimates.

Aim 5. Does genital herpes infection in pregnancy, if untreated, increase the risk of PTD and LBW, compared to no genital herpes infection? (untreated vs. controls without genital herpes) .

Point and interval estimates of the hazard ratio for PTD associated with untreated genital herpes, vs. no infection, will be calculated as described above, using Cox regression (Cohort C vs. D). The approach to inclusion of potential confounders, modeling continuous covariates, and model diagnostics is as described above.

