database, we will identify those who are treated with anti-herpes medications (e.g., acyclovir). Thus, four comparators in Stage I samples of all mother-birth dyads (N=90,000) will be established based on the information on genital herpes infection and its treatment and timing of the treatment (see **Figure 1**): pregnant women with genital herpes who are treated *before* the 3rd trimester (Cohort A), pregnant women with genital herpes who are treated *after* the 3rd trimester (Cohort B), women with genital herpes, but untreated (Cohort C), and women with neither genital herpes nor receiving anti-herpes medications (Cohort D). We will also randomly select 300 pregnant women from each of the four cohorts for Stage II sampling to conduct telephone interviews to ascertain more detailed medical history of genital herpes infections (for Cohorts A, B & C), compliance with prescribed medication treatment during pregnancy (Cohorts A & B), and potential confounders including risk factors for PTD and LBW (for all Cohorts). The questions in the Specific Aims will be addressed using the Cox proportional hazards regression model in analyses of PTD analysis, accommodating delayed entry into the cohort and time-dependent covariates⁴⁵⁻⁴⁷, and logistic regression in analyses of LBW. The analysis will incorporate the large sample size from Stage I (all 90,000 births) and rich information on additional confounders and compliance from Stage II interviews. The schematic description of the two-stage study design and cohorts is presented in Figure 1.

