3.3.3 Populations

Stage I population

All KPNC women aged 18 years (the minimum age required by our KPNC IRB) or older who are pregnant beyond 20 weeks of gestation during the recruitment period will be included to form the Stage I population, estimated at 90,000. These women will be assigned to one of the four cohorts based on diagnosis and treatment of genital herpes infection. Identification of genital herpes will be based on information from multiple databases captured by KPNC EMR including clinical diagnosis, laboratory testing and viral culture, prenatal screening inventory, and medical history. Treatment will be determined through prescription and dispensing of anti-herpes medications from the pharmacy data. Based on the combination of infection and treatment as well as the specific aims, we expect to establish four cohort groups. information currently available information, we expect a total of 2,100 women with genital herpes receiving treatment before the 3rd trimester (Cohort A), 2,100 women with genital herpes receiving treatment after the 3rd trimester (Cohort B), 6,600 women with untreated genital herpes (Cohort C), and 79,200 controls with neither genital herpes nor treatment (Cohort D), as shown in Figure 1. A small adjustment may need to be made at the end of pregnancy, if the status of the infection and/or treatment has changed since the initial assignment to each comparator (e.g., from untreated to treated). Through the KPNC EMR, we will have information on genital herpes infection and treatment during pregnancy (the exposure variables), and PTD and LBW (the outcome variables) (Table 4) as well as many potential confounders (Table 5) for all 90,000 pregnant women. This large Stage I population will provide a large powerful study population to examine comparative effectiveness of genital herpes treatment in reducing adverse pregnancy outcomes, addressing the questions listed in the specific aims.

Stage II samples

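### Low birthweight (LBW) is analysed by logistic regression on final cohort status, with no gestational-age alignment of treatment: with no true effect, this tilts Aim 1 towards treatment and Aim 2 against early treatment

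*Combined protocol and SAP*

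**What the plan says.** For preterm delivery (PTD), the plan deals with the timing of treatment. Section 3.1 describes the Cox analysis as "accommodating delayed entry into the cohort and time-dependent covariates". Section 4.2 adds under Aim 2: "Treatment will be handled as a time-varying covariate for proper classification of exposure status in each risk set for the Cox regression". Under Aim 3, the duration and dose metrics are "treated as time-dependent covariates in Cox regression analyses to account for changes in exposure status during follow-up".

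For LBW, section 4.2 gives one sentence covering Aims 1 to 5: "Analyses of LBW as the outcome will parallel those described above for PTD, but logistic regression techniques will be used rather than Cox regression". The propensity-score version in section 4.3 is conditional logistic regression stratified on score deciles. Neither section states a landmark, gestational-age matching or a still-pregnant condition for LBW.

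Cohort membership is not fixed at entry. Women enter beyond 20 weeks (section 3.3.1), and section 3.3.3 says: "A small adjustment may need to be made at the end of pregnancy, if the status of the infection and/or treatment has changed". Its example is a move from untreated to treated, and the Stage II text leaves final exposure status to the analysis stage. The expected counts include "2,100 women with genital herpes receiving treatment after the 3rd trimester (Cohort B), 6,600 women with untreated genital herpes (Cohort C"). Section 3.4 makes clear that Cohort B means treatment begun during the 3rd trimester.

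**The concern.** A woman can join Cohort B only if she is still pregnant when her 3rd-trimester treatment starts. An infected woman who would have been treated late but delivers first is classified as untreated, in Cohort C. Early delivery and LBW go together, so B loses early LBW births and C keeps them. This happens even if treatment does nothing.

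Three contrasts are affected:

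- **Aim 1 (A+B vs C):** the treated side is depleted of early LBW births and the untreated side is enriched, so treatment looks beneficial.
- **Aim 2 (A vs B):** A keeps its early deliveries and B has none before its start, so early treatment looks worse. Cohort C plays no part. The bias runs against the study's own hypothesis.
- **Aim 5 (C vs D):** the enriched C looks worse than the uninfected. The effect is small because C is large.

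LBW is one of the study's two outcomes, and the results are meant to inform treatment recommendations. Part of an apparent LBW effect could come from how the cohorts are formed. Adjusting for confounders or for the propensity score does not remove this, because it is misclassified follow-up time and not a baseline imbalance.

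**Working it through.** **Inputs from the documents.** Cohort sizes are A 2,100, B 2,100, C 6,600 and D 79,200 (section 3.3.3). LBW is 8–10%, the test is two-sided at 0.05, and the effective size is 1,200 per cohort (section 4.5).

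**Input assumed.** f is the share of LBW births that precede Cohort B's treatment start. The documents do not give it.

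**1. The plan's own figures.** I used a likelihood-ratio power approximation with 2,400 vs 1,200 for Aim 1 and 1,200 vs 1,200 for Aims 2 and 5, reading the Table 6 rate as the overall rate. At LBW 8% / 10% the detectable odds ratios are 0.70 / 0.72 (Aim 1), 0.65 / 0.68 (Aim 2) and 1.53 / 1.47 (Aim 5). Table 6 prints .70 / .72, .65 / .68 and 1.54 / 1.47. The sizes are therefore read as the plan intends.

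**2. How many women change class.** 2,100 / (2,100 + 6,600) = 24% of infected women not treated before the 3rd trimester end in B.

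**3. Expected LBW risk by final cohort with no effect of infection or treatment** (L = overall LBW):

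- rA = rD = L
- rB = L(1 − f) / (1 − L·f)
- rC = (8,700·L − 2,100·rB) / 6,600
- rAB = (rA + rB) / 2

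Example with L = 8% and f = 10%:

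- rB = 0.072 / 0.992 = 7.26%
- rC = (696 − 152.4) / 6,600 = 8.24%
- rAB = 7.63%
- Aim 1 OR = 0.0826 / 0.0898 = 0.92
- Aim 2 OR = 0.0870 / 0.0783 = 1.11
- Aim 5 OR = 0.0898 / 0.0870 = 1.03

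**4. False-positive rate.** This uses a Wald test on the log odds ratio. In the same example for Aim 1 with 2,400 vs 1,200, the standard error is √(1/169.1 + 1/90.7) = 0.130 and z = −0.083 / 0.130 = −0.64, so the test rejects 9.8% of the time. With Stage I counts (4,200 vs 6,600) the standard error is 0.073, z = −1.13, and it rejects 20.5% of the time; at L = 10% this becomes 24%.

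| f | Null OR, Aims 1 / 2 / 5 | False positives, Aim 1 | Aim 2 | Aim 5 |
|---|---|---|---|---|
| 5% | 0.96 / 1.05 / 1.02 | 6–10% | 6–8% | 5–7% |
| 10% | 0.92 / 1.11 / 1.03 | 10–24% | 11–17% | 6–12% |
| 20% | 0.84 / 1.25 / 1.07 | 26–72% | 29–54% | 7–33% |

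Each range runs from the 1,200-per-cohort rule at L = 8% to Stage I counts at L = 10%. Under the 1,200 rule alone, Aim 5 stays at 5–8%. The formulas assume that no normal-weight birth precedes B's start. If 2% of them do, the f = 10% odds ratios for Aims 1 and 2 soften to about 0.93 and 1.09.

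**5. What f might be.** With assumed gestation and LBW-by-week curves:

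- B starts spread over 28–32 weeks give f of 3–17%, Aim 1 OR 0.86–0.98 and Aim 2 OR 1.03–1.20.
- B starts spread over 28–37 weeks give f of 11–38%, Aim 1 OR 0.71–0.92 and Aim 2 OR 1.11–1.58.

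**6. Does alignment remove it?** In simulations with no effect:

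- Comparing starters with women still pregnant and not yet treated at the same gestational age gives OR 0.99–1.01 for Aims 1 and 2.
- A 28-week landmark gives about 1.00 for early treatment, and about 1.00 for infected women not treated by the landmark against D.
- Dropping later starters after the landmark does not work for Aim 5. Across two sets of assumed curves, the OR stays at 1.06–1.08 (unaligned 1.07–1.09) for starts at 28–37 weeks, and at 1.15–1.19 (unaligned 1.15–1.20) for starts at 36–37 weeks.

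**The case against.** The strongest reply is that this is an under-specified sentence and not a stated wrong method. The authors know that treatment must be time-updated, and running LBW in parallel could be meant to carry that over. This stands in part: the fault lies in what the text omits. But the time-updating language is tied to Cox risk sets, and logistic regression has none unless they are built. Followed as written, the text uses final status.

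Two further points have weight. Tables 4 and 5, which hold the outcome and confounder definitions, were not in the text available for this review. The preliminary LBW result in section A.2 is described as independent of PTD. If LBW is in fact analysed among term births only, the bias disappears when every start precedes 37 weeks, though not for later starts. Section 4.2 does not state such a restriction. Section 3.3.3 calls the status adjustment small, but 24% of infected women not treated early must end in B.

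Three stronger readings are tempting, and the documents do not support them:

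- **The bias is known to be large.** Section A.3 mentions treatment recommended after 36 weeks, and placing all B starts at 36–37 weeks gives Aim 1 ORs of 0.51–0.82. That passage describes general practice and does not say when Cohort B women start. This is an outer bound only.
- **Aim 5 is seriously compromised.** At f = 10% its null OR is 1.03, against a detectable 1.47–1.54.
- **PTD shares the fault.** It does not, if the Cox model is run as described.

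**Conclusion.** The point holds and should be fixed before analysis, with Aims 1 and 2 leading and Aim 5 minor. Given final-status classification in an unaligned logistic model, the direction follows from how the cohorts are formed. Confidence that this will happen is moderate, because the LBW text is brief and two tables could not be checked.

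The size is conditional on f. The bias is slight if Cohort B starts cluster early in the 3rd trimester and larger if many are late. At f = 20% the Aim 1 null OR of 0.84 is still weaker than the detectable .70–.72 in Table 6, but the false-positive rate is already 26–72%. The calculation takes the plan's expected cohort sizes and LBW rate, no true effect, and no normal-weight births before B's start.

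**What to change.** State in sections 4.2 and 4.3 that LBW exposure is aligned on gestational age:

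- **Early treatment:** use a landmark at the start of the 3rd trimester. Among women still pregnant then, compare those treated before it with those not yet treated.
- **3rd-trimester starts, and A vs B:** use sequential landmarks or day-of-start risk sets in which both groups are still pregnant at the same gestational age.
- **Aim 5:** compare infected women not treated by the landmark with Cohort D women still pregnant at the same landmark. State that this exposure includes women treated later (about 24% by the plan's counts). Do not exclude later starters, because that conditions on the future and leaves the bias almost unchanged.
- **Propensity score:** estimate it at the same time points.
- **Term restriction:** if LBW is meant to be analysed independently of PTD, say so and still align the starts.

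The cost is SAP text, programming, a decision on how aligned sets enter the semiparametric likelihood estimation, and a statement of the changed estimands. The LBW rows of Table 6 must be restated, with lower precision for late-start contrasts. The early contrast is somewhat diluted, because its comparator includes women treated later. No new data are needed: the pharmacy and birth records already planned supply the dates.
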